### ***Analysis of all treatment-emergent adverse events***

The following TEAE summaries will be generated for the safety population.

- Overview of TEAEs, summarizing number (%) of patients with any
  - TEAE
  - Treatment-emergent SAE
  - TEAE leading to death
  - TEAE leading to permanent treatment discontinuation.
- All TEAEs by primary SOC, HLGT, HLT, and PT, showing number (%) of patients with at least one TEAE sorted by the SOC internationally agreed order. The other levels (HLGT, HLT, PT) will be presented in alphabetical order.
- All TEAEs by primary SOC and PT, showing the number (%) of patients with at least one TEAE, sorted by the internationally agreed SOC order and by decreasing incidence of PTs within each SOC. This sorting order will be applied to all other tables, unless otherwise specified.
- All TEAEs regardless of relationship and related by primary SOC, HLGT, HLT and PT, showing the number (%) of patients with at least one TEAE, sorted by the internationally agreed SOC order. The other levels (HLGT, HLT, PT) will be presented in alphabetical order.
- All TEAEs by maximal severity, presented by primary SOC and PT, showing the number (%) of patients with at least one TEAE by severity (ie, mild, moderate, or severe), sorted by the sorting order defined above.

### ***Analysis of all treatment emergent serious adverse event(s)***

- All treatment-emergent SAEs by primary SOC, HLGT, HLT, and PT, and also by primary SOC and PT, showing the number (%) of patients with at least one treatment-emergent SAE, sorted by the internationally agreed SOC order. The other levels (HLGT, HLT, PT) will be presented in alphabetical order for the 4-level summary.

### ***Analysis of all treatment-emergent adverse event(s) leading to treatment discontinuation***

- All TEAEs leading to treatment discontinuation, by primary SOC, HLGT, HLT, and PT, and also by primary SOC and PT, showing the number (%) of patients sorted by the internationally agreed SOC order. The other levels (HLGT, HLT, PT) will be presented in alphabetical order for the 4-level summary.

### ***Analysis of AESIs***

Summaries of AESIs ([Section 2.1.4.1](#)) include:

- All treatment emergent AESIs, by AESI category and PT, showing number (%) of patients, sorted by decreasing incidence of PT within each AESI category.
- Within each treatment emergent AESI category, at a minimum, the data display will include:
  - Overview summary
  - Treatment duration summary
  - Incidence by patient and by event
  - Treatment emergent SAEs
  - TEAEs leading to treatment discontinuation
  - TEAEs leading to death
  - Possibly related TEAEs

#### **2.4.5.2 Deaths**

The incidence of death, if applicable, will be generated on the safety population:

- Number (%) of patients who died by study period (on-treatment, during follow-up or post-study)
- Death in included but not treated patients
- TEAE leading to death (death as an outcome on the AE CRF page as reported by the Investigator) by primary SOC , HLG, HLT and PT, and by primary SOC and PT, showing number (%) of patients sorted by internationally agreed order of SOC and alphabetic order of HLG, HLT, and PT for the 4-level summary.

Listings will be provided for all deaths with flags indicating on-treatment, during follow-up or post-study status.

#### **2.4.5.3 Analyses of laboratory variables**

The summary statistics (including number, mean, median, SD, minimum and maximum) of all laboratory variables (laboratory values and changes from baseline) will be calculated for each visit or study assessment (baseline, each post-baseline time point, endpoint) by dose regimen cohort. This section will be organized by biological function as specified in [Section 2.1.4.4](#).

In addition, for all laboratory parameters, the mean value and mean change from baseline at each scheduled visit will be plotted by dose regimen cohort.

The incidence of PCSAs ([Appendix A](#)) at any time during the TEAE period will be summarized by biological function and dose regimen cohort whatever the baseline level and/or according to the following baseline status categories:

- Normal/missing
- Abnormal according to PCSA criterion or criteria.

For lipids, the NCEP APTIII classification will be used for the baseline.

The incidence of PCSAs at any time during the post-study period will be summarized by the actual dose regimen cohort received in the 12-week core treatment period.

The incidence of abnormal laboratory values at any time during the TEAE period will be summarized in shift tables by biological function and dose regimen cohort whatever the baseline level and/or according to the following baseline status categories:

- Normal/Missing
- Abnormal high according to the normal range
- Abnormal low according to the normal range

Listings will be provided with flags indicating the out of range values as well as the PCSA values.

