#### 2.4.5 Analyses of safety data

Safety data will be summarized descriptively for each study [REDACTED] separately. The summary of safety results will be presented by dose regimen cohort. Further subdivision by weight group will be performed only for selected parameters given the small sample size.

Safety summaries during the entire TEAE period will be provided. In addition, summaries on the important safety events will also be provided by time periods including 0-12 weeks, 0-24 weeks, and 0-52 weeks; details are provided in [Section 2.4.5.6](#). For the analyses on 0-52 weeks and entire TEAE period, summaries on the non-selected doses will only include the data collected prior to the first dose adjustment to the selected dose; a combined 'any dose' group will be added to summarize all the safety data for all treated patients. In addition, data after the dose adjustment will be summarized separately ([Section 2.4.11](#)).

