##### *General common rules*

All safety analyses will be performed on the safety population as defined in [Section 2.3.2](#), unless otherwise specified, using the following common rules:

- The baseline value is defined as the last available value prior to the first dose of the study medication.
- The potentially clinically significant abnormality (PCSA) values are defined as abnormal values considered medically important by the Sponsor according to predefined criteria/thresholds based on literature review and defined by the Sponsor for clinical laboratory tests and vital signs ([Appendix A](#)).

- PCSA criteria will determine which patients had at least 1 PCSA during the TEAE period, taking into account all evaluations performed during the TEAE period, including nonscheduled or repeated evaluations. The number of all such patients will be the numerator for the on-treatment PCSA percentage.
- The treatment-emergent PCSA denominator by group for a given parameter will be based on the number of patients assessed for that given parameter in the TEAE period by dose regimen cohort on the safety population.
- For quantitative safety parameters based on laboratory measurements, descriptive statistics will be used to summarize result and change from baseline values by visit and dose regimen cohort. Summaries will include the endpoint value. The endpoint value is commonly defined as the value collected at the same day/time of the last dose of IMP. If this value is missing, this endpoint value will be the closest one prior to the last dose intake.
- Analyses of the safety variables will be essentially descriptive and no systematic between-group testing is planned.

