#### **2.4.5.1 Analyses of adverse events**

##### ***Generalities***

The primary focus of AE reporting will be on TEAEs. Pretreatment and post-study AEs will be described separately.

If an AE date/time of onset (occurrence, worsening, or becoming serious) is incomplete, an imputation algorithm will be used to classify the AE as pretreatment, treatment-emergent, or post-study. The algorithm for imputing date/time of onset will be conservative and will classify an AE as treatment emergent unless there is definitive information to determine it is pretreatment or post-study. Details on classification of AEs with missing or partial onset dates are provided in [Section 2.5.3](#).

Adverse event incidence tables will present the number (n) and percentage (%) of patients in each dose regimen cohort experiencing an AE by primary SOC (sorted by internationally agreed SOC order), HLG, HLT, and PT, sorted in alphabetical order. Multiple occurrences of the same event in the same patient will be counted only once in the tables within a treatment phase. The denominator for computation of percentages is the safety population within each dose regimen cohort. In addition, the incidence and the number of events per 100 patient-years (number of events adjusted for the total duration of exposure) will be provided for AE summaries during the entire TEAE period.

Sorting within tables ensures the same presentation for the set of all AEs within the observation period (pretreatment, treatment-emergent, and post-study). For that purpose, the table of all TEAEs presented by primary SOC and PT sorted by the internationally agreed SOC order and

decreasing frequency of PTs within SOCs will define the presentation order for all other tables unless otherwise specified. Sorting will be based on results for the selected dose regimen cohort.

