### ***Neutrophils***

The incidence of neutropenia will be summarized by maximal grade (lowest absolute neutrophil count reported during the TEAE period):

- Grade 1:  $\geq 1.5$  Giga/L-LLN
- Grade 2:  $\geq 1.0$  Giga/L-1.5 Giga/L
- Grade 3:  $\geq 0.5$  Giga/L-1.0 Giga/L
- Grade 4:  $< 0.5$  Giga/L

For patients with Grade 3 or 4 neutropenia, a listing with the individual neutrophil counts, WBC counts, platelet counts, lymphocytes, and hemoglobin at each visit (including re-tests taken at either central or local labs) will be provided.

The neutrophil counts at each scheduled visit during the study will be plotted by dose regimen cohort. In addition, summaries will include the following data: discontinuation, restart dosing, dosing delay, number of episodes, and normalization (to  $>1$  x LLN or return to baseline if baseline  $< LLN$ ). Laboratory measurements during the post-study period will be considered in the analysis of normalization.

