#### **2.4.5.4 Analyses of vital sign variables**

The summary statistics (including number, mean, median, SD, minimum, and maximum) of all vital signs variables (vital signs values and changes from baseline) will be calculated for each visit or study assessment (baseline, each post-baseline time point, endpoint) by dose regimen cohort. The average of the two SBP and the two DBP readings for a patient at a particular visit will be used for analysis.

The incidence of PCSAs at any time during the TEAE period will be summarized by dose regimen cohort whatever the baseline level and/or according to the following baseline status categories:

- Normal/Missing
- Abnormal according to PCSA criterion or criteria

Listings will be provided with flags indicating the PCSA values.

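### Whole-period laboratory and vital-sign abnormality percentages are not comparable between regimens: non-selected regimens are cut at dose adjustment, and no exposure adjustment is written for these tables

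*SAP*

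**What the plan says.** SAP 2.4.5.3 states that the incidence of laboratory PCSAs "at any time during the TEAE period will be summarized by biological function and dose regimen cohort whatever the baseline level". SAP 2.4.5.4 has the same form for vital signs: "The incidence of PCSAs at any time during the TEAE period will be summarized by dose regimen cohort whatever the baseline level". The General common rules of SAP 2.4.5 count patients, not tests or time: "The treatment-emergent PCSA denominator by group for a given parameter will be based on the number of patients assessed for that given parameter". Repeat and unscheduled tests can supply the abnormal value. Cytopenias are graded by the worst value. For neutrophils, "The incidence of neutropenia will be summarized by maximal grade (lowest absolute neutrophil count reported during the TEAE period"; platelets and lymphocytes follow the same pattern.

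SAP 2.4.5 then gives regimens different observation lengths. For 0-52 weeks and the entire TEAE period, "summaries on the non-selected doses will only include the data collected prior to the first dose adjustment to the selected dose". It adds a combined group over all doses and reports post-adjustment data separately. It also says that "summaries on the important safety events will also be provided by time periods including 0-12 weeks, 0-24 weeks, and 0-52 weeks", with details in SAP 2.4.5.6. That section is not in the text available for review.

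Exposure adjustment appears in SAP 2.4.5.1, where "the incidence and the number of events per 100 patient-years" "will be provided for AE summaries during the entire TEAE period". For laboratory data the only related wording is under Hepatic disorders, where showing PCSAs by length of exposure is optional. Protocol 11.4.3 leaves the exposure-adjusted safety analyses to the SAP.

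**The concern.** The share of patients with at least one abnormal value rises with the number of times each patient is tested, even when the risk at each test is the same. A patient who stays on the selected regimen is tested to Week 156, or to Week 96 in the third portion. A patient on a non-selected regimen contributes only up to the switch, which Protocol Table 1 places anywhere from Week 16 to Week 144. Columns set side by side by regimen then mix risk with length and frequency of observation.

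Neutropenia, thrombocytopenia and ALT elevation are among the events of special interest in Protocol 10.4.4.1. A low percentage in a column with little follow-up could be read as better tolerability of that regimen. The AE tables carry a rate that guards against this. In the visible text the laboratory and vital-sign tables do not.

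**Working it through.** The documents give no draw count or PCSA rate, so there is no stated figure to reproduce. I counted scheduled post-baseline hematology tests for completers.

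**Inputs**
- Core phase (Protocol 9.3.4): Weeks 2, 4, 6, 8, 10 and 12, plus one test before the second dose: 6 + 1 = 7 in every portion. Not counted: a Regimen 3 patient whose extra test is local also has a central sample at Day 8.
- Extension, portions 1 and 2, selected regimen (Protocol 10.1.9.1 and 10.1.10): 14 visits (V13 to V26) plus EOT = 15.
- Extension, third portion (Protocol 10.1.9.3): 6 visits (Weeks 24, 36, 48, 60, 72, 84) plus EOT = 7.
- Switch (Protocol 10.1.9 and Table 1): at the next scheduled visit after selection, V13 (Week 16) to V26 (Week 144). The pre-dose sample at that visit still counts before adjustment.

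**Draws**
- Selected regimen, portions 1 and 2: 7 + 15 = 22.
- Third portion: 7 + 7 = 14. Ratio between portions 22/14 = 1.57.
- Pooled selected regimen, taking 36 portion 1-2 patients (18 evaluable per weight group) and 28 third-portion patients, all completing: (36 × 22 + 28 × 14)/64 = 1184/64 = 18.5.

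| Switch of a non-selected patient | Draws before switch | 22 ÷ draws | 18.5 ÷ draws |
|---|---|---|---|
| Week 16 | 8 | 2.75 | 2.31 |
| Week 24 | 10 | 2.20 | 1.85 |
| Week 48 | 13 | 1.69 | 1.42 |
| Week 144 | 21 | 1.05 | 0.88 |

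Other parameters, selected portion 1-2 completer against a Week 16 switcher: chemistry 6 + 15 = 21 against 6 + 1 = 7, ratio 3.0. Vital signs, EOS visit included: 3 + 14 + 1 + 1 = 19 against 3 + 1 = 4, ratio 4.75.

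**Effect on an ever/never percentage.** Assume the same abnormality probability p at every draw, independent draws, and no true difference between regimens. Then P(at least one) = 1 − (1 − p)^k for k draws. The values of p are assumptions; the documents give none. The pooled column is (36 × P(22) + 28 × P(14))/64.

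| p per draw | 22 draws | 14 draws | Pooled selected | 13 draws | 8 draws |
|---|---|---|---|---|---|
| 0.5% | 10.4% | 6.8% | 8.8% | 6.3% | 3.9% |
| 1% | 19.8% | 13.1% | 16.9% | 12.2% | 7.7% |
| 2% | 35.9% | 24.6% | 31.0% | 23.1% | 14.9% |
| 5% | 67.6% | 51.2% | 60.5% | 48.7% | 33.7% |

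**Fixed windows.** In 0-12 weeks every portion has 7 scheduled draws, ratio 1.0. In 0-52 weeks the selected regimen has 7 + 6 = 13 (portions 1 and 2) or 7 + 3 = 10 (third portion), against 8 for a Week 16 switcher. The largest ratio is 13/8 = 1.63, so that window is still unequal.

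**The case against.** The strongest reply is that the remedy may already be planned. SAP 2.4.5 promises 0-12, 0-24 and 0-52-week summaries of important safety events. SAP 2.4.5.6 and the Appendix C mock-up tables, which would show whether PCSAs and worst grades are among them, are not in the available text. This stands: one cannot say that laboratory data lack a balanced-window table. But such windows would not correct the entire-TEAE tables, and 0-52 weeks stays unequal.

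The second reply is that little depends on these tables. Dose selection uses Week 12 data (Protocol 6.1.2.4), before any truncation at dose adjustment. The analyses are descriptive, with no between-group tests planned. Each non-selected regimen has about 12 patients. By-visit summaries, plots and listings are also planned. This limits the consequence, but by-visit means do not show how often a worst grade occurs, and readers will still compare the percentage columns.

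The third reply is that constant, independent risk exaggerates the gap. If abnormalities arise early or recur in the same patients, the shared core draws capture most of them. This also stands. It narrows the gap and makes the percentages above illustrative.

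**Conclusion.** The point holds in a limited form. In the visible SAP, PCSA incidence and worst cytopenia grade over the entire TEAE period, and over 0-52 weeks if tabulated there, are crude percentages of patients by regimen with unequal numbers of assessments and no exposure adjustment. A non-selected regimen with early switching can look safer at equal risk per draw.

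For hematology the ratio is at most about 2.75 against a portion 1-2 completer and about 2.3 against the pooled selected regimen. These counts assume completers and scheduled tests only; dropout and unscheduled tests would change them.

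A reader might infer more than the documents support:
- That non-selected regimens look safer by construction. The gap depends on when the dose is selected. If three regimens run in sequence, with at least 6 weeks of data per escalation step and then Week 12 data, the first Regimen 1 patients cannot switch before about 6 + 6 + 12 = 24 weeks, where the ratio is 2.2. At a Week 144 switch it is 1.05, and 0.88 against the pooled column, so the direction can reverse.
- That the portions differ threefold. For hematology they differ 1.57-fold, and the third portion, all on the selected regimen, narrows the regimen gap.
- That the plan has no balanced laboratory comparison. The available text cannot settle this.

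**What to change.** In SAP 2.4.5.3 and 2.4.5.4:
- Add to the entire-TEAE tables of PCSAs and worst cytopenia grade, and to any 0-52-week versions, the number of patients with a first event per 100 patient-years at risk on that regimen, and the number of assessments per patient.
- State that comparison between regimens on PCSAs and worst grade rests on the already planned 0-12-week window.
- Confirm that these parameters are included in the time-period summaries of SAP 2.4.5.6. If they are, a cross-reference is enough for this part.

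The cost is SAP wording and a few extra table columns, with no new data. The downside is that the comparison window is short, so late abnormalities would be described by regimen rather than compared.

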Fasting lipids including total cholesterol, high density lipoprotein cholesterol, low density lipoprotein cholesterol, and triglycerides will be tested at Visit 1 (Day -28 to Day -1, up to 31 days), Visit 8 (Week 4), Visit 12 (Week 12) during the initial core treatment phase and at designated visits during the extension phase ([Section 1.2.2](#)). Patients are required to fast at least 8 hours before the test.

The HbA1c evaluation will only be performed at the Screening based on the patient's medical history and the Investigator's judgment.

- High sensitivity C-reactive protein (hs-CRP) will be evaluated at Visit 1 (Day -28 to Day -1, up to 31 days), the Baseline Visit 2 (Week 0, Day 1), Visit 7 (Week 2), Visit 8 (Week 4), Visit 9 (Week 6), Visit 10 (Week 8), Visit 11 (Week 10), Visit 12 (Week 12) during the initial core treatment phase and at designated visits during the extension phase (see [Section 1.2.2](#)).

Blood samples for ANA/anti double-stranded deoxyribonucleic acid (dsDNA) antibody will be collected at the Baseline Visit 2 (Week 0, Day 1), Visit 12 (Week 12) during the initial core treatment phase and at designated visits during the extension phase (see [Section 1.2.2](#)).

Erythrocyte sedimentation rate (ESR) will be measured at Visit 2 (Week 0, Day 1), and Visit 12 (Week 12) during the initial core treatment phase and at designated visits during the extension phase (see [Section 1.2.2](#)).

Pregnancy test: For females who have commenced menstruating, a serum pregnancy test should be performed at the Screening and the urine pregnancy test should be tested locally at Visit 2 (Week 0, Day 1), Visit 8 (Week 4), Visit 10 (Week 8), and every visit from Visit 12 (Week 12) to Visit 27 EOT (Week 156 for dose-finding and second portions/Week 96 for third portion).

- Optional: Based on patient's family and medical history, the Investigator's judgment, EBV IgG and IgM, hepatitis B and C screening: HBs-Ag, hepatitis B surface antibody (HBs-Ab), total hepatitis B core antibody (HBc-Ab), and hepatitis C antibody (HCV-Ab) may be performed at the Screening Visit 1 (Day -28 to Day -1, up to 31 days). The HIV serology may be performed only based on the Investigator's assessment for those HIV suspected patients. Some tests defined as optional may be required according to local regulations.

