10.6.7 Management of dyslipidemia

Patients treated with tocilizumab have been observed to have increased elevations of all lipid parameters, including low density lipoprotein (LDL) cholesterol. A similar finding has been observed for sarilumab. The potential for dyslipidemia in pcJIA patients treated with IL-6R antagonists is unknown. Patients who are found to have dyslipidemia during the course of the study should refer National Cholesterol Education Program (NCEP) Expert Panel Report on Blood Cholesterol levels in Children and Adolescents and refer to applicable local guideline for the standard care of treatment ([24](#)).

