Total Cholesterol	All age ranges	≥6.20 mmol/L or 240 mg/dL	CF = g x 2.58 = mmol Based on normal ranges: 45 to 182 mg/dL (1-3 years), 109 to 189 mg/dL (4-6 years), 126 to 191 mg/dL (Boys 6-9 years), 122 to 209 mg/dL (Girls 6-9 years), 130 to 204 mg/dL (Boys 10-14 years), 124-217 mg/dL (Girls 10-14 years), 114 to 198 mg/dL (Boys 15-19 years), 125 to 212 mg/dL (Girls 14-19 years)
Triglycerides	All age ranges	≥4.0 mmol/L or 350 mg/dL	After >12 hours of fast) CF = g x 1.14 = mmol Based on normal ranges: 30 to 86 mg/dL (Boys 0-5 years), 32 to 99 mg/dL (Girls 0-5 years), 31-108 mg/dL (Boys 6-11 years), 35 to 114

**CRITERIA for POTENTIALLY CLINICALLY SIGNIFICANT ABNORMALITIES  
For Studies in Children**

Parameter	Age range	PCSA	Comments
			mg/dL (Girls 6-11 years), 36 to 138 mg/dL (Boys 12-15 years), 43 to 138 mg/dL (Girls 12-15 years), 40 to 163 mg/dL (Boys 16-19 years), 40-128 mg/dL (Girls 16-19 years)
Lipase	All age ranges	≥2 ULN	Based on normal ranges: 3 to 32 U/L (1-18 years)
Amylase	All age ranges	≥2 ULN	Based on normal ranges: 10 to 30 U/L (NN), 10 to 45 U/L (1-18 years)
Glucose	All age ranges	Hypoglycaemia <2.7 mmol/L or 50 mg/dL Hyperglycaemia ≥7 mmol/L or 120 mg/dL (fasted after >12 hours of fast); ≥10.0 mmol/L or 180 mg/dL (unfasted)	CF = g x 5.55 = mmol Based on normal ranges: 50 to 90 mg/dL (NN), 60 to 100 mg/dL (Child)
CRP	All age ranges	>2 ULN or >10 mg/L (if ULN not provided)	Based on normal ranges: <6 mg/L
Hematology			Common Terminology Criteria for Adverse Events v3.0 (CTCAE), 2006 ; Division of Microbiology and Infectious Diseases Pediatric Toxicity Tables, 2007 ; Division of AIDS Table for Grading the Severity of Adult and Pediatric Adverse Events, 2004; Mulberg AE et al. Pediatric Drug Development Concepts and applications. John Wiley & sons, Inc. 2009; Family Practice Notebook, LLC, 2012; Tietz NW et al. Clinical Guide to Laboratory Testing, 3 rd edition 1995
WBC	Birth/0 to 27 days old (Neonates)	<4.0 GIGA/L or 4,000 /mm  >25.0 GIGA/L or 25,000 /mm 	To be used if no differential count available
	28 days/1 month to 23 months old (Infants)	<4.0 GIGA/L or 4,000 /mm  >20.0 GIGA/L or 20,000 /mm 	
	24 months/2 years to <6 years old (Children)	<3.0 GIGA/L or 3,000 /mm  >16.0 GIGA/L or 16,000 /mm 	Based on normal ranges: 9,000 to 30,000 /mm  (birth), 9,400 to 38,000 /mm  (0-1

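### The lipid PCSA tables use one cholesterol and one triglyceride limit for all ages and none for LDL, and their baseline scheme and fasting condition differ from the paediatric report and fasting rule the protocol cites elsewhere

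*SAP*

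**What the plan says.** SAP section 2.4.5.3 tabulates PCSAs over the treatment-emergent period by biological function and dose regimen cohort, overall or by baseline status. On that status it adds "For lipids, the NCEP APTIII classification will be used for the baseline". Protocol section 11.4.3 has the same sentence. The label is not expanded in either document and is in neither abbreviation list and neither reference list.

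The on-treatment limits are in SAP Appendix A: "≥6.20 mmol/L or 240 mg/dL" for total cholesterol and "≥4.0 mmol/L or 350 mg/dL" for triglycerides, each for all ages. The comment cells of the same rows print normal ranges by age and, for most bands, by sex. The triglyceride comment carries the condition "After >12 hours of fast". The rows run from total cholesterol to triglycerides to lipase, with no row for LDL or HDL and no redaction mark between them. SAP section 2.1.4.4 lists both LDL and HDL among the fasting lipids measured.

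On fasting, protocol section 9.3.4 says: "Patients are required to fast at least 8 hours before the test". For patients who develop dyslipidemia, protocol section 10.6.7 points to the "National Cholesterol Education Program (NCEP) Expert Panel Report on Blood Cholesterol levels in Children and Adolescents".

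**The concern.** Lipid elevation is an expected effect of this drug class. Protocol section 4.2 names raised LDL among the adult findings, section 8.8.5 says cholesterol will be watched closely, and section 10.6.7 says the effect in pcJIA is unknown. The PCSA tables are where a reader looks for how many children had a marked elevation.

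For lipids, those tables have four weaknesses:

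- They cannot count LDL elevations at all.
- For cholesterol and triglycerides, a flag demands a larger excess over normal in some age bands than in others.
- Baseline status follows a scheme other than the paediatric report cited for the same patients.
- A triglyceride sample taken after 8 to 12 hours of fasting complies with the protocol but falls outside the row's stated condition, and no rule says how to treat it.

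**Working it through.** **1. Do the two units of each limit agree?** Appendix A gives the cholesterol conversion as "CF = g x 2.58 = mmol" and the triglyceride factor as 1.14.

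- Cholesterol: 2.40 g/L × 2.58 = 6.19 mmol/L (stated 6.20).
- Triglycerides: 3.50 g/L × 1.14 = 3.99 mmol/L (stated 4.0).

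Both agree after rounding.

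**2. How far above normal is each limit?** Ratio = PCSA limit ÷ upper normal limit printed in the same row. Gap = limit − upper normal limit.

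| Cholesterol band | Upper limit (mg/dL) | 240 ÷ upper limit | Gap (mg/dL) |
|---|---|---|---|
| 1–3 y | 182 | 1.32 | 58 |
| 4–6 y | 189 | 1.27 | 51 |
| Boys 6–9 y | 191 | 1.26 | 49 |
| Girls 6–9 y | 209 | 1.15 | 31 |
| Boys 10–14 y | 204 | 1.18 | 36 |
| Girls 10–14 y | 217 | 1.11 | 23 |
| Boys 15–19 y | 198 | 1.21 | 42 |
| Girls 14–19 y | 212 | 1.13 | 28 |

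| Triglyceride band | Upper limit (mg/dL) | 350 ÷ upper limit | Gap (mg/dL) |
|---|---|---|---|
| Boys 0–5 y | 86 | 4.07 | 264 |
| Girls 0–5 y | 99 | 3.54 | 251 |
| Boys 6–11 y | 108 | 3.24 | 242 |
| Girls 6–11 y | 114 | 3.07 | 236 |
| Boys 12–15 y | 138 | 2.54 | 212 |
| Girls 12–15 y | 138 | 2.54 | 212 |
| Boys 16–19 y | 163 | 2.15 | 187 |
| Girls 16–19 y | 128 | 2.73 | 222 |

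The youngest band has the largest ratio for both lipids, but the fall is not even. Girls 6–9 (1.15) sit below boys 10–14 (1.18) and boys 15–19 (1.21) for cholesterol. Among girls, the triglyceride ratio rises again from 2.54 to 2.73.

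**3. What could this do to the counts?** This is an illustration only, because the documents do not give the size of the rise in children. Assume cholesterol is normally distributed, the printed range covers the central 90% or 95%, and every value rises by the same percentage. At ages 4–6 the midpoint is (109 + 189)/2 = 149 and the SD is 40/1.645 = 24.3 or 40/1.96 = 20.4. After a 20% rise the mean is 178.8 and the SD is 29.2 or 24.5.

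- Above 189: 1 − Φ(10.2/29.2) = 36%, or 1 − Φ(10.2/24.5) = 34%.
- At or above 240: 1 − Φ(61.2/29.2) = 1.8%, or 1 − Φ(61.2/24.5) = 0.6%.

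| Assumed rise | Ages 4–6: above upper limit | Ages 4–6: flagged | Girls 10–14: above upper limit | Girls 10–14: flagged |
|---|---|---|---|---|
| 10% | 13–17% | 0.03–0.2% | 13–17% | 2–5% |
| 20% | 34–36% | 0.6–1.8% | 33–36% | 11–15% |
| 30% | 56–57% | 4–7% | 55–56% | 28–31% |

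The two bands exceed their own upper limits about equally often, yet are flagged at different rates.

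**4. Which planned outputs do cover LDL?** SAP section 2.4.5.3 plans by-visit values and changes, mean plots, shift tables against the normal range, and listings flagging out-of-range values, for all laboratory variables. The documents do not say whether that normal range is age-specific. The lipid category in SAP Table 5 searches reported adverse events, and protocol section 10.4.2 lets a laboratory value become an adverse event only under listed conditions.

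**The case against.** **Flat limits can be deliberate.** SAP section 2.4.5 defines PCSAs as sponsor thresholds for medically important values, drawn from the literature and not tied to multiples of normal. Appendix A uses one limit for all ages elsewhere too (sodium, calcium, platelets). This stands, and it is why the flat limits need not be removed. The same appendix does set blood pressure, creatinine and white-cell limits by age, and ALT, AST and ALP limits as multiples of the upper limit, so either approach would be in keeping with it.

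**The lipid effect is described elsewhere.** The outputs in step 4 cover every lipid, LDL included, so under-flagging of the whole lipid analysis should not be inferred. SAP section 2.4.5.6, on additional safety methods, is not in the public text and may add more.

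**Stronger readings that the documents do not support:**

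- A reader might infer that lipid outcomes are classed by an adult scheme, or that children high for their age fall into an acceptable class. The sentence governs baseline status only, and the documents neither expand the label nor give its categories. What they show is a mismatch with the paediatric report.
- A reader might infer that Group B will look safer than Group A. PCSAs are tabulated by dose regimen cohort, weight-group splits are kept for selected parameters that do not name lipids in the available text, and weight is not age.
- A reader might infer that the fasting mismatch hides elevations. Protocol section 10.1 says non-fasting could overestimate LDL and triglycerides, so a shorter fast would tend to add flags.

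**Conclusion.** The point holds for the PCSA tables and the baseline class, and no further. One cholesterol limit and one triglyceride limit serve all ages, at 1.11–1.32 and 2.15–4.07 times the table's own upper normal limits. LDL, the lipid singled out in the adult findings, has no criterion, so its PCSA incidence cannot be produced. The baseline scheme is not the paediatric report the protocol cites, although that citation concerns care and not tabulation, so this is a mismatch and not a contradiction. The fasting conditions, more than 12 hours against at least 8, do not agree.

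The ratios rest only on figures printed in Appendix A. The percentages in step 3 rest on an assumed distribution and an assumed rise, and show direction, not expected counts. Safety analysis is descriptive, so no test or sample size is affected. This is a cheap improvement to the tables.

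**What to change.** All changes concern tabulation; none bears on the care of a patient with raised lipids.

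1. In SAP section 2.4.5.3 and protocol section 11.4.3, replace NCEP APTIII with the paediatric NCEP source cited in protocol section 10.6.7 (protocol reference 24), and add it to the SAP references.
2. Add an LDL row to Appendix A with a threshold from that source. Appendix A prints no LDL range to build on, and the documents do not reproduce the report, so the sponsor must confirm that it has usable categories for LDL and the other lipids to be classed.
3. Set the fasting condition in the triglyceride row to at least 8 hours. Protocol section 10.1 already has fasting duration recorded for centrally performed tests.
4. Keep the flat cholesterol and triglyceride limits, and add a supplementary count of patients with an on-treatment value above the age- and sex-specific upper limit printed in Appendix A. State which band applies at age 6 and, for girls, at age 14, where the printed cholesterol bands overlap.

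The cost is SAP table edits, a matching one-sentence protocol change, a few more tables and flags, and less direct comparability with the adult programme. No new data are needed.
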